### 3. Abstract:

Respiratory insufficiency is the most common cause of morbidity and mortality in neuromuscular diseases. A hallmark of many neuromuscular diseases is progressive respiratory insufficiency and an eventual dependence upon assisted ventilation. Inspiratory muscle training (IMST) is a potential treatment option that has been shown to increase strength and ventilatory function in critically ill, difficult to wean adults and in patients with mild neuromuscular weakness. However, it is poorly understood whether breathing function can be modified by IMST, in patients with neuromuscular disease and symptomatic ventilatory insufficiency. The proposed study measures IMST-induced changes in ventilatory function in adults with neuromuscular disease, and whether strength gains translate to improved resting ventilation. Patients will undergo IMST exercises, 3-5 days per week for up to 3 months. Outcome variables include measures of change in pulmonary function, muscle strength and ventilatory pattern.

### 4. Background:

Inherited neuromuscular diseases (NMDs) include muscular dystrophies, motor neuron diseases, metabolic myopathies, or other congenital myopathies. Although the genetic etiology, pathophysiology, and disease course varies vastly between the inherited neuromuscular diseases, a commonality is a progressive loss of ventilatory muscle function. Respiratory muscle dysfunction increases the rate of pulmonary complications and death and is a major factor in respiratory failure. Respiratory failure is the primary cause of mortality for most INMDs.

Ventilation is a mechanical process, where the respiratory muscles function as a pressure pump to drive inspiratory airflow and increase the lung volume. Patients with neuromuscular diseases typically present with a restrictive pulmonary pattern, where compliance is reduced by muscle weakness and a stiffened chest wall, creating increased mechanical loads at baseline and intensifying neuroventilatory drive. When the efferent neuromuscular drive is consistently unmet by sufficient ventilatory motor output, the mismatch is perceived as dyspnea and clinically appears as hypoventilation and hypercapnia. In chronic, progressive neuromuscular disease, the principal determinant of ventilatory insufficiency is weakness of the respiratory muscles.

The principal strategies to attenuate chronic ventilatory insufficiency are to reduce the load of breathing, to strengthen the capacity of the respiratory muscles, or a combination of the two approaches. Medications, positioning aids or assisted ventilation have been used to reduce breathing loads in NMDs. With recent advances in pharmacological therapies and the use of assisted ventilation, survival to age 30 may exceed 80% in Duchenne muscular dystrophy

(DMD). Nevertheless, assisted strategies do not prevent or reverse expected declines in longer-term ventilator function that occur over the clinical course of progressive neuromuscular disorders. In fact, the preponderance of the literature has shown that MV independently facilitates diaphragm muscle atrophy and contractile dysfunction, known as ventilator-induced diaphragmatic dysfunction.

Alternatively, respiratory muscle training may improve muscle function and delay ventilatory decline. It has been previously asserted that inspiratory muscle training (IMT) could overwork the respiratory muscles and induce fatigue in patients with neuromuscular compromise. However, the literature does not support this assumption. Among the NMDs, the majority of IMT research has been conducted in children and young adults with DMD who do not require assisted ventilation. Training-induced strength gains tend to occur more slowly in patients with neuromuscular diseases. IMT has shown effective for increasing muscle strength and endurance, regardless of disease severity. However, patients with the greatest baseline ventilatory function make the largest gains in forced expiratory maneuvers. Additionally, breathing loads are perceived as lighter by patients, following ventilatory muscle training. Patients with DMD make greater strength gains when training with high-pressure overloads, compared to low-modest resistive breathing, and have shown long term improvement in MIP, VC, and max ventilation for as long as two years.

Because previous research has primarily trained adolescents and young adults, additional knowledge is needed regarding the ability of the respiratory muscles to remodel in our youngest and older patients. Therefore, we plan to include two separate age cohorts to address these gaps. Our team safely incorporated IMST into the clinical care of critically-ill, mechanically ventilated infants with and without neuromuscular disease, including a neonate who sustained a cerebrovascular accident and an infant with Pompe disease and sepsis. We report that the intervention is both feasible and safe in infants (Smith, under review, Phys Ther). Additionally, our group has reliably assessed respiratory strength and function in boys with DMD ranging from 4 through 10 years of age (Mathur, Physiother Canada, 2009). A key objective of our laboratory is to identify the stage of disease where the greatest therapeutic benefit can be achieved. The literature suggests this could occur with earlier intervention when possible (McCool, 1995, Phys Ther), but older adults with a milder disease phenotype also stand to gain from training.

While the findings of IMT show initial promise for patients with DMD, less is known about the ability of patients with other NMDs to respond to training. In particular, the role of IMT is virtually unknown among the rare or orphan neuromuscular diseases (i.e. metabolic and other congenital myopathies). Although a common attribute of the neuromuscular compromise is the predominance of respiratory insufficiency, the pathology, clinical signs, onset and response to medical management varies vastly between NMD diagnoses. For example, patients with Pompe disease may be distinguished from other NMDs by a relatively earlier involvement of ventilatory over limb muscle weakness. Moreover, ventilatory muscle weakness and pulmonary function correlate poorly with ambulatory function in Pompe disease. Therefore, we may not be able to apply the research in DMD directly to other progressive neuromuscular disorders.

The pattern of ventilatory muscle weakness especially differs between the NMDs. Pulmonary pressures typically decline prior to a loss of forced expiratory volumes in neuromuscular disease, making strength a more sensitive index of pulmonary function. While vital capacity may decline by >8% per year in DMD after the age of 12, inspiratory strength remains preserved to a greater degree than expiratory strength. In DMD and amyotrophic lateral sclerosis, maximal inspiratory and expiratory pressures correlate equally with unassisted cough peak

[figure not shown]
flows. In contrast, the rate of decline in global ventilatory function varies vastly between adults with Pompe disease, but is characterized by predominant diaphragm muscle weakness. Intercostal and diaphragm muscle involvement are differentially affected among spinal muscular atrophy variants and may not occur at all in the mildest, adult-onset genotype.

Because the inspiratory and expiratory muscles can both be affected by neuromuscular disease, the relative roles of training either function may be examined. The expiratory muscles primarily influence the effectiveness of cough flows, which are vital for mucociliary clearance and prevention of respiratory infection. On the other hand, a functional inspiratory pump is necessary in the inspiratory phase of cough, in order to achieve an appropriate cough volume. Moreover, diaphragmatic weakness results in chronic hypoventilation and pre-empts a need for ventilatory assist. Because the diaphragm is particularly weakened by assisted ventilation and disuse, we propose to conduct a pilot study of the specific role of inspiratory muscle strength training (IMST) in respiratory muscle strength and ventilatory function. We have extensive experience in evaluating respiratory muscle strength and pulmonary function in the laboratory and the clinic, and our group provides clinical post-operative IMST in difficult to wean infants and children with neuromuscular diseases.

[figure not shown]

## **5. Specific Aims:**

- To identify the effect of IMST on the strength of inspiratory and expiratory muscles, in patients with neuromuscular disease and ventilatory insufficiency.
- To determine whether IMST-associated changes in strength are associated with differences in tidal and forced pulmonary function.
- To compare the rate and extent of training response, based upon disease diagnosis and baseline function.

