### **Design**

Patients will be considered eligible for IMST if they have been diagnosed with an inherited neuromuscular disease and show clinical evidence of impaired pulmonary function. Subjects will undergo RMST for up to 12 weeks. Pulmonary function and strength testing and a symptom questionnaire will be administered before and after IMST.

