### **Study Procedures**

Complete respiratory testing will occur before and after IMST. In conjunction with respiratory testing, baseline and exertional blood pressure, heart and respiratory rate, end-tidal CO2 and pulse oximetry will be monitored. The following tests will be completed on all subjects.

**Pulmonary Function Tests:** Subjects will complete tidal flow-volume assessments and forced expiratory maneuvers according to American Thoracic Society guidelines. Three to five trials will be administered, separated by at least 2 minutes of rest.

**Repeated Inspiratory Load Compensation:** Subjects will undergo 4 sets of 10 maximal-effort breaths against standardized resistances (one set each at 0, 5, 10, and 15 cm H2O). If a patient cannot generate at least 20% of resting tidal volume with one of the lower standardized resistances, we will forego testing with any higher loads. Trials will be separated by at least three minutes of rest.

**Maximal Respiratory Pressures:** Subjects will perform maximal inspiratory and expiratory pressure maneuvers, in accordance with American Thoracic Society testing guidelines. Trials will be administered until 5% variability is achieved between three trials (typically achieved within 5 trials), and separated by at least 2 minutes of rest.

Every attempt will be made to assist participants and their families to travel to University of Florida for respiratory testing. If the study team determines that it is not in the best interest of the eligible participant to travel for a test session, the study team will consider the option of conducting the requisite tests at a site local to the subject.

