### **Statistical Methods**

The primary endpoints for inspiratory muscle training efficacy will include respiratory muscle strength. Secondary outcome measures include be respiratory function and breathing pattern during loaded breathing.

Changes in strength and respiratory function will be analyzed by repeated measures ANOVA.

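### The stated ANOVA does not estimate the strength-function association in Aim 2, and two tests per patient give no rate of response distinct from extent for Aim 3

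*Combined protocol and SAP*

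**What the plan says.** Section 5 (Specific Aims) sets three aims. The first is the effect of training on strength. The second is "To determine whether IMST-associated changes in strength are associated with differences in tidal and forced pulmonary function". The Abstract puts the same question as "whether strength gains translate to improved resting ventilation". The third is "To compare the rate and extent of training response, based upon disease diagnosis and baseline function".

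The Statistical Methods make respiratory muscle strength primary, and respiratory function and breathing pattern under load secondary. They name one model: "Changes in strength and respiratory function will be analyzed by repeated measures ANOVA". Study Sample adds that up to thirty patients will be analysed by baseline severity, judged by pulmonary function relative to prediction for age. No analysis by diagnosis is described.

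On timing, Design says "Pulmonary function and strength testing and a symptom questionnaire will be administered before and after IMST" and "Subjects will undergo RMST for up to 12 weeks". Study Procedures agrees: "Complete respiratory testing will occur before and after IMST". No intermediate strength or function test is scheduled, and rate is not defined.

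**The concern.** An aim about association needs an estimate of association. Repeated measures ANOVA of each outcome answers a different question: did the mean move? Followed as written, the plan would report one mean change in strength and one in function. It could not say whether the patients who became stronger are those whose breathing improved, which is the question the Abstract poses.

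An aim about rate needs either a response curve or a definition. One test before and one after give a single difference per patient. Two patients with the same gain, one responding early and one late, look identical. Any reported rate would be extent divided by time under another name.

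**Working it through.** The documents give no alpha, power, effect size or SD, so there is no planned figure to reproduce. Only the sample size (up to 30, with 20-30 mentioned for similar studies), the two tests, the training limit of 12 weeks and the six disease classes come from the protocol. The other inputs are assumptions.

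**Aim 2: what the ANOVA can see.** With two time points, the time effect is the squared paired t: F = n × (mean change / SD of change)². With n = 30 and a mean change of 0.5 SD, F = 30 × 0.25 = 7.5 on 1 and 29 df, p = 0.010. The correlation r between the strength and function changes does not enter the formula. The slope of function change on strength change, in SD units, does depend on it, with SE = √((1 − r²)/28) and t = 2.048:

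| r between changes | ANOVA, each outcome | Slope (95% CI) |
|---|---|---|
| 0 | F = 7.5, p = 0.010 | 0 (−0.39 to 0.39) |
| 0.5 | F = 7.5, p = 0.010 | 0.50 (0.17 to 0.84) |
| 0.8 | F = 7.5, p = 0.010 | 0.80 (0.57 to 1.03) |

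**Aim 2: precision available.** By Fisher's z, tanh(atanh 0.5 ± 1.96/√(n − 3)) gives 0.17 to 0.73 at n = 30 and 0.07 to 0.77 at n = 20. At two-sided 5% and 80% power, the detectable correlation is tanh(2.802/√(n − 3)): 0.49 at n = 30 and 0.59 at n = 20. These figures are for one unadjusted association.

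**Aim 3: can rate be told from extent?** Let g(w) be the share of the 12-week gain reached by week w: w/12 if linear, or (1 − e^(−w/τ))/(1 − e^(−12/τ)) if exponential. At week 4, g = 33% (linear), 45% (τ = 12 weeks), 56% (τ = 6) and 75% (τ = 3). All four curves give the same before and after values.

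If every patient is tested at the same duration, change per week is a constant multiple of change (correlation 1). If durations vary independently of the change, and the mean change equals its SD, the correlation is 1/√(1 + 2c²), where c is the coefficient of variation of 1/duration:

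| Duration (uniform) | c² | Formula | Simulation, n = 30 |
|---|---|---|---|
| 10-12 weeks | 0.0028 | 0.997 | 0.997 |
| 8-12 weeks | 0.0138 | 0.987 | 0.987 |
| 4-12 weeks | 0.1047 | 0.909 | 0.913 |

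What little differs from extent partly reflects test time. On one and the same curve, the ratio of change per week at week 8 to that at week 12 is 1.5 × g(8): 1.00 (linear), 1.15 (τ = 12), 1.28 (τ = 6) and 1.42 (τ = 3). At week 10 it is 1.2 × g(10): 1.00, 1.07, 1.13 and 1.18.

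**Aim 3: baseline function and diagnosis.** If change is regressed on the same measure's own baseline, with no training effect at all, the expected slope is reliability − 1. Assumed reliabilities of 0.80 to 0.95 give −0.20 to −0.05. For diagnosis, 30/6 = 5 patients per listed class on average, at most.

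**The case against.** The strongest reply is that this is a declared pilot without a power calculation, that Aim 1 and the primary strength endpoint are untouched, and that both changes are measured in the same patients, so the association can be computed later. All of that is true. A reader might infer that the trial cannot answer Aim 2 at all, and the documents do not support that: the gap is in the stated analysis, not in the data. But pilot status excuses wide intervals, not an aim without an estimator. ANOVA could carry a change-in-strength covariate, yet none is stated.

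On rate, training response could be read as progression of training load, since the Training section describes supervised sessions at least weekly at which load is advanced. That reading is possible but not stated. Load is not an outcome, the section does not say it is recorded, and it depends on tolerance and on the investigator's decisions as well as on strength.

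Two further inferences go too far. One is that a reported rate would rank patients by when they were tested. The documents say only that training may last up to 12 weeks and do not suggest a wide spread. With a modest spread, the correlations of 0.987 to 0.997 mean that ranking would follow extent almost entirely. The other is that the severity analysis has no scale. Study Sample refers to age prediction and sets its eligibility cut-offs in percent of predicted, so that scale is reasonably readable. What is missing is the choice of measure.

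**Conclusion.** The point holds and should be fixed. The Aim 2 result is algebraic: with two time points, the time test for each outcome is the same whatever the correlation between the changes. The 0.5 SD change only illustrates it, and I read differences in function in Aim 2 as before-to-after changes. For Aim 3, the two scheduled tests cannot separate speed from extent. Change per week is either an exact multiple of the change or nearly so (correlation about 0.91 even if durations run evenly from 4 to 12 weeks), and if durations differ it also depends on test time unless gain is linear. The correlations rest on assumed durations unrelated to response, and the ratios on assumed curves.

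Mean changes in strength and function remain reportable. Extent by baseline severity is planned but needs a named measure. Extent by diagnosis has no stated analysis, and the numbers allow description only.

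**What to change.** 1. **Aim 2.** Name in advance one tidal and one forced measure. The plan already provides both pressures ("Subjects will perform maximal inspiratory and expiratory pressure maneuvers"), so regress change in each named measure on change in maximal inspiratory pressure and, separately, on change in maximal expiratory pressure. Use percent predicted where reference values exist. Adjust for the baseline function value, the baseline pressure and age group. Report slopes with 95% CIs as exploratory. State that measurement error in the pressure change pulls the slope towards zero.

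2. **Aim 3, rate.** Delete the word. Alternatively, if training load is recorded at the supervised sessions, report it only as an exploratory description of training progression, not as a strength outcome.

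3. **Aim 3, extent.** Use a time-by-baseline term on one named continuous measure that is not the response, for example baseline FVC percent predicted when the response is a change in pressure. Note that regression to the mean may remain, because patients can qualify on low values and there is no control group. Report results by diagnosis descriptively.

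**Cost.** Items 1 and 3, and deleting rate, are changes of wording and analysis on tests already scheduled. Reporting training load may need added data capture. The statistical price is imprecision. There are four main slopes (two measures by two pressures), and each model has five parameters including the intercept, leaving 30 − 5 = 25 residual df at most, or 15 at 20 patients. Intervals will therefore tend to be wide, and should be presented as such.

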## **6. IMST Research Plan:**

### **Hypothesis**

Inspiratory muscle strength training (IMST) will significantly improve maximal inspiratory pressure and pulmonary function in patients with neuromuscular disease and respiratory muscle contractile dysfunction.

### **Design**

Patients will be considered eligible for IMST if they have been diagnosed with an inherited neuromuscular disease and show clinical evidence of impaired pulmonary function. Subjects will undergo RMST for up to 12 weeks. Pulmonary function and strength testing and a symptom questionnaire will be administered before and after IMST.

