### **Study Sample**

This study will consist of two groups of male and female patients aged 6 months-65 years with a confirmed diagnosis of a neuromuscular disease. Group 1 will consist of children with earlier-onset disease, aged 6 months through 11 years of age upon inclusion. Group 2 will consist of patients aged 12 through 65 years, which will include both patients with later-stage, early onset disease, and those with late-onset, milder disease. The inherited neuromuscular disease classifications include: muscular dystrophies, motor neuron diseases, neuromuscular junction diseases, peripheral nerve diseases, metabolic myopathies, or other congenital myopathies that fall into the NIH classification of a rare/orphan disease. In addition, patients will demonstrate evidence of at least one of the following signs of respiratory insufficiency: (1) decreased FVC <80% of age and gender-predicted, (2) decreased maximal inspiratory pressure <80% of age and gender-predicted, (3) decreased maximal expiratory pressure <80% of age and gender-predicted, (4) any routine use of supplemental oxygen or mechanically-assisted ventilation, or (5) patient report of functionally-limiting dyspnea.

We plan to enroll up to thirty subjects and analyze the data according to baseline disease severity (age-predicted pulmonary function). No power calculation is feasible for this pilot trial; however, similar studies have found significant training differences in strength with 20-30 patient cohorts. Patients will be ineligible to participate if they have required acute antibiotic therapy for an acute respiratory infection within 15 days prior to baseline screening, were prescribed systemic corticosteroids or neuromuscular blocking agents within 15 days of the baseline screening, show laboratory evidence of hepatic or hematologic failure, are currently participating in other research studies involving investigational drugs, have a diagnosis of a primary

pulmonary disease, use tobacco products, or have any other concurrent medical condition which, in the opinion of the investigators, would make the subject inappropriate to participate in the respiratory exercises.

Subjects will be recruited from other research studies conducted by the PI and Sub-Is, the neuromuscular clinic run by the study team, or by self-referral. The study will be listed on ClinicalTrials.gov and the research team's website.

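### The single-arm before-after change is framed as an effect of IMST, and the primary endpoint is plural and open

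*Combined protocol and SAP*

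**What the plan says.** Section 6, Training, gives IMST to all subjects for up to three months. The two groups in Study Sample are age cohorts, not treatment arms. No control, sham, run-in or repeated baseline is described. On timing, Design says: "Pulmonary function and strength testing and a symptom questionnaire will be administered before and after IMST". Study Procedures repeats the same two occasions.

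The wording of what will be learned is stronger:

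- Abstract: "The proposed study measures IMST-induced changes in ventilatory function in adults with neuromuscular disease".
- Specific Aims, Aim 1: "To identify the effect of IMST on the strength of inspiratory and expiratory muscles".
- Hypothesis: "Inspiratory muscle strength training (IMST) will significantly improve maximal inspiratory pressure and pulmonary function in patients with neuromuscular disease".
- Statistical Methods ties the primary endpoints to training efficacy, and Possible Benefits pairs efficacy with feasibility.

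Aim 2 is more careful and speaks of IMST-associated changes. Background and Study Sample both call the study a pilot.

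Statistical Methods refers to primary endpoints in the plural and says that they will include respiratory muscle strength. It names no variable, unit or contrast. The analysis is one sentence: repeated measures ANOVA of change. On size, Study Sample says: "We plan to enroll up to thirty subjects and analyze the data according to baseline disease severity". It gives no power calculation, SD or effect size.

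**The concern.** With one arm and two occasions, the time effect in the ANOVA is the total of everything that moved the mean between the two sessions. Several things other than training can move it. MIP and MEP are maximal-effort manoeuvres, so practice can raise them. MIP, MEP or FVC below 80% of predicted are among the entry routes, so some baseline values will be low by chance and will rise on retest. Other care may change. Background says of these diseases that "a commonality is a progressive loss of ventilatory muscle function", which pushes the other way.

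Followed as written, the plan would let a significant rise be reported as IMST efficacy when part or all of it came from elsewhere. A real gain could equally be masked by decline. Separately, an open primary endpoint lets the choice between MIP and MEP be made after the data are seen.

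**Working it through.** **1. What the analysis estimates.** The plan has no figure of its own to reproduce. For one arm tested twice:

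mean change = training + learning + regression to the mean + other care + disease course.

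There is one observed quantity and five unknowns. Testing whether the sum is zero does not test whether the first term is zero. Adding age group, diagnosis or baseline severity as a between-subject factor does not help, because everyone in every stratum is trained.

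**2. The open primary endpoint.** Study Procedures yields two strength measures, MIP and MEP. Alpha is not stated; I assume two-sided 5%, which is 2.5% in the favourable direction. If either may count:

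- independent: 1 − 0.975² = 0.049;
- correlation 0.6 (assumed), bivariate normal: 0.044.

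Two-sided, the independent case is 1 − 0.95² = 0.0975.

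**3. How sensitive the test is to drift (illustration only).** All inputs here are assumed except n. n = 30 is the plan's maximum, and n = 20 is the lower end of the similar cohorts that Study Sample mentions.

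- SD of change = SD × √(2(1 − reliability)), with an assumed between-patient SD of 20 to 25 points of % predicted MIP and reliability of 0.80 to 0.90.
- Low: 20 × √0.2 = 8.9. High: 25 × √0.4 = 15.8.

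Chance of a significant rise with no training effect (noncentral t, paired test, two-sided 5%, upper tail):

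| Net upward drift (points) | SD 15.8, n = 20 | SD 8.9, n = 30 |
|---|---|---|
| 0 | 2.5% | 2.5% |
| 1 | 4.5% | 8.6% |
| 3 | 12.4% | 42.7% |
| 5 | 26.9% | 84.1% |

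**4. Regression to the mean (illustration only).** Suppose entry were solely by MIP below 80% of predicted, judged on the baseline test itself. The expected rise on retest is (1 − r) × SD × φ(a)/Φ(a), with a = (80 − source mean)/SD. Take an assumed SD of 25:

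- source mean 60, r = 0.95: 0.05 × 25 × 0.290/0.788 = 0.5 points;
- source mean 80, r = 0.80: 0.20 × 25 × 0.399/0.500 = 4.0 points.

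The real figure would be smaller, since patients may enter by other routes.

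**5. Disease course.** The only rate in the documents is for vital capacity in Duchenne muscular dystrophy (DMD): "While vital capacity may decline by >8% per year in DMD after the age of 12". The same sentence adds that inspiratory strength is better preserved than expiratory strength, while another in that part of Background says pressures usually fall before volumes. The documents therefore do not settle a rate for MIP, and I do not carry this one over.

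**The case against.** The strongest reply is that this is an uncontrolled pilot across rare diseases, openly labelled as such, with a power calculation disclaimed and Aim 2 already worded as association. That stands. A single-arm pilot is a reasonable design, and no control arm is being asked for. The Abstract and Possible Benefits are not analysis rules either. But pilot status supports preliminary wording; it does not support efficacy or a promise of significant improvement, and the plan contains no statement of the limitation.

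A second reply is that learning may be small. Pressure trials are repeated until three agree within 5%, and "Subjects will be recruited from other research studies conducted by the PI and Sub-Is, the neuromuscular clinic run by the study team", so some patients will know the tests. Both may reduce learning; neither removes learning between sessions or can be checked without a control.

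A third is that decline makes any observed gain conservative. That holds only if decline outweighs learning, regression to the mean and other care together, which this design cannot show.

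A fourth is that respiratory muscle strength, read with Aim 1, plausibly means MIP and MEP, and that the inflation is modest. Both are fair. The Hypothesis, however, names MIP with pulmonary function and not MEP, so the sections do not agree on what is primary.

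Two stronger readings are tempting. A reader might infer from the drift table that a false finding of benefit is likely. The documents give no learning effect, SD or reliability, so the table shows sensitivity, not a probability for this trial. A reader might also apply the DMD vital-capacity rate to 12 weeks of MIP; the passage that gives the rate does not support that.

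**Conclusion.** The concern holds in a limited form. The design can show change in mean strength over the training period but cannot attribute it to IMST, and Aim 1, the Hypothesis and Statistical Methods are worded as if it could. This conclusion rests on the text alone and needs none of the assumed figures. The direction of the net bias is unknown and its size cannot be derived from the documents.

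The open primary endpoint raises the favourable-direction error from 2.5% to about 4.4–4.9%, assuming a two-sided 5% test and two unadjusted endpoints. That is modest, but avoidable. The point should be fixed; it does not make the pilot unsound.

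**What to change.** 1. **Statistical Methods, endpoint.** Name change in MIP from the pre-IMST to the post-IMST test session as the single primary endpoint, in line with the Hypothesis, and state one unit. Make MEP, pulmonary function and breathing pattern under load secondary. If MIP and MEP are to stay co-primary to match Aim 1, state an adjustment such as Holm. If % predicted is the unit, report patients without a predicted value separately in cm H2O and state how many there are.
2. **Statistical Methods, conclusion.** Report mean change with its 95% CI. Add that, with no control group, this is change over the training period; that it may include test learning, regression to the mean, other care and disease course; and that it is preliminary evidence rather than an estimate of IMST efficacy.
3. **Abstract, Specific Aims, Hypothesis and Possible Benefits.** Align the wording, for example to change over the IMST period.

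Cost: text changes only, with no added patients, tests or visits and no change to eligibility. The claim becomes weaker. MEP loses co-primary standing or, with Holm, the smaller of the two p-values must fall below 0.025. If % predicted is used, some of the youngest patients (enrolment starts at 6 months of age) may drop out of the pooled primary analysis, which lowers n by a number the documents do not give. The change does not remove the bias; it stops the bias being reported as efficacy.
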